#### **2.1.3 Efficacy endpoints**

Response assessments were to be performed on a monthly basis using IMWG criteria (Rajkumar. 2011) and included:

- M-protein quantification (serum and 24-hr urine)
- Serum free light chain levels
- Corrected serum calcium

In case of plasmacytoma at baseline, radiological evaluations were to be performed every 3 cycles or when clinically indicated (i.e., to confirm a progression).

In case of bone lesions at baseline, bone lesion evaluations were to be performed when clinically indicated or to confirm a response or progression. Bone marrow biopsy/aspiration was to be performed to confirm a sCR or CR.

An independent adjudication committee (IAC) independently assessed clinical response using the IMWG response criteria.

Biological responses ( $\geq$ PR) and progression were to be confirmed on 2 consecutive biological (serum and/or urine M protein) disease assessments. No confirmation was required for radiological assessment.

##### ***2.1.3.1 Primary efficacy endpoint(s)***

The primary efficacy endpoint is ORR, defined as the proportion of patients with sCR, CR, VGPR or PR as best overall response (BOR) as assessed by the IAC. The BOR will be derived using disease assessments performed from the start of treatment through the entire study excluding any assessments performed after the cutoff date or following the start of further therapies for MM.

The ordering of evaluations from best to worse is: sCR, CR, VGPR, PR, MR, stable disease (SD), progressive disease (PD), not evaluable (NE). BOR for patients without response assessment by the IAC will be 'Not evaluable'.

Subgroup analyses of BOR using IAC assessment will be performed for the variables listed in [Table 4](#).

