8.1.2 Dose of Drug per Administration

Isatuximab will be administered once every week (QW) in Cycle 1 (4 weeks) followed by once every other week (Q2W) in subsequent cycle until unacceptable toxicity, disease progression, withdrawal of consent and/or Investigator's decision ([Section 1.2](#)). Cycle N day 1 corresponds to cycle N-1 day 29.

For dose level and schedule, refer to [Section 6.2.1](#).

The initial rate of infusion of isatuximab will be 175 mg/hour.

- First infusion:
Initiate infusion rate at 175 mg/hour. In the absence of infusion associated reaction after 1 hour of infusion, increase the rate by 50 mg/hour increments every 30 minutes, to a maximum of 400 mg/hour.
- Subsequent infusions:
Initiate infusion rate at 175 mg/hour. In the absence of infusion associated reaction after 1 hour of infusion, increase the rate by 100 mg/hour increments every 30 minutes, to a maximum of 400 mg/hour.

recovered, the infusion may be restarted at one half of the original infusion rates. If symptoms do not recur after 30 minutes, the infusion rate may be increased in 50 mg/hour increments every 30 minutes, to a maximum of 400 mg/hour.

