9.3 EFFICACY

9.3.1 Criteria for Response

ORR is defined as the proportion of patients with stringent complete response (sCR), complete response (CR), very good partial response (VGPR), and partial response (PR) based on responses as assessed using the International Myeloma Working Group (IMWG) Uniform Response Criteria (see [Appendix C](#)). Response evaluation will be performed on a monthly basis. The best overall response for each patient will be determined by independent adjudication committee.

All responses (sCR, CR, VGPR, PR) should be confirmed on 2 consecutive laboratory efficacy parameters assessments according to study flow-chart (approximately 4 weeks interval). Stable disease (SD) does not require confirmation. Disease progression by paraprotein should be confirmed on within the first 4 weeks after last assessment. Disease progression based on imaging, bone marrow plasma cell percentage, or hypercalcemia (not attributable to any other cause) do not need to be confirmed.

Clinical benefit rate (CBR): defined as the proportion of patients with sCR, CR, VGPR, PR or MR according to IMWG criteria.

Duration of response (DOR): defined as the time from the date of the first response to the date of subsequent progressive disease (PD) or death, whichever happens earlier. In the absence of the confirmation of subsequent disease progression or death before the analysis cut-off date, the DOR will be censored at the date of the last valid assessment performed before the analysis cut-off date or date of initiation of new anticancer treatment, whichever is earlier. DOR is determined only for

patients who have achieved a response of \geq PR. DOR will not be calculated for patients that do not achieve a response.

Overall survival (OS): defined as the time interval from the date of first study treatment administration to death due to any cause. In the absence of the confirmation of death before the analysis cutoff date, OS will be censored at the last date the patient is known to be alive or at the study cutoff date, whichever is earlier.

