11.1 PERMANENT TREATMENT DISCONTINUATION WITH INVESTIGATIONAL MEDICINAL PRODUCT(S)

11.1.1 List of Criteria for Permanent Treatment Discontinuation

Patients may withdraw from treatment with IMP if they decide to do so, at any time and irrespective of the reason, or this may be done at the discretion of the Investigator. All efforts should be made to document the reason for discontinuation and this should be documented in the e-CRF.

Treatment with the IMP should be discontinued in any of the following cases:

- At the patient's request, at any time and irrespective of the reason (consent's withdrawal).
- If, in the Investigator's opinion, continuation of the study treatment would be detrimental to the patient's wellbeing, such as:
 - Disease progression.
 - Unacceptable AE.
 - Poor compliance to the study protocol.
 - Any other reason such as intercurrent illness that prevents further administration of study treatment (will be specified).
- Patient is lost to follow-up.
- Sponsor decision to discontinue the study.

If patients are clinically stable, and possibly deriving clinical benefit from therapy with minimal toxicity, the patient will be maintained on treatment for the maximum period of time defined in [Section 6.6.3](#).

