#### **2.1.3 Efficacy endpoints**

All efficacy endpoints are defined as secondary objectives.

Disease assessments are performed every cycle by the Independent Adjudication Committee (IAC) using the IMWG criteria. The assessment of “Progressive disease” by the site doctor (collected in e-CRF) will not be used for phase 1 in efficacy analysis.

The following efficacy endpoints will be derived for the phase 1 part of the study.

Best overall response (BOR): defined as the best sequential response in every cycle’s assessment from the start of treatment through the entire study excluding any time point following the start of other treatment for MM. The ordering of evaluations from best to worse is: stringent complete response (sCR), complete response (CR), very good partial response (VGPR), partial response (PR), minimal response (MR), stable disease (SD), progressive disease (PD), not evaluable (NE). Confirmation of response is needed.

Overall survival (OS): defined as the time interval from the date of first study treatment administration to death due to any cause. In the absence of the confirmation of death before the analysis cutoff date, OS will be censored at the last date the patient is known to be alive or at the study cutoff date, whichever is earlier.

Progression free survival (PFS): defined as the time interval from the date of first study treatment administration to the date of the first assessed disease progression or death due to any cause, whichever comes first. In the absence of disease progression, death before the analysis cutoff date or death before the date of initiation of new anticancer treatment, PFS will be censored at the earliest of the date of the last valid assessment not showing disease progression performed before initiation of new anticancer treatment or the analysis cutoff date, whichever is earlier.

Duration of response (DOR): DOR is defined as the time from first response that is subsequently confirmed to the first documented tumor progression or death. If progression or death is not observed, the date of the last valid disease assessment performed before cutoff date or initiation of

a new anticancer treatment will be used. DOR is determined only for patients who have achieved a response of  $\geq$  PR and will not be calculated for patients who did not achieve a response.

Time to response (TTR): TTR is defined as the time from first dose to first response (PR or better) that is subsequently confirmed.

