#### **2.1.3.2 Secondary efficacy endpoint(s)**

Secondary efficacy endpoints are defined below.

- Duration of Response (DOR) (in weeks): DOR is defined as the time from the date of the first IAC determined response ( $\geq$  PR) that is subsequently confirmed, to the date of first IAC determined PD or death, whichever happens earlier (if reported before the analysis cut-off date or the date of initiation of a new anticancer treatment). If progression and death are not observed before the analysis cut-off date or the date of initiation of new anticancer treatment, DOR will be censored at the earliest of the date of the last valid disease assessment not showing disease progression performed prior to initiation of a further anticancer treatment or the analysis cut-off date. DOR is determined only for patients who have achieved a confirmed response of  $\geq$ PR.
- Clinical benefit rate (CBR): defined as the proportion of patients with sCR, CR, VGPR, PR or MR as BOR according to IMWG criteria, as determined by the IAC.
- Progression free survival (PFS) (in months): defined as the time interval from the date of first isatuximab administration to the date of the first IAC-confirmed disease progression or the date of death due to any cause, whichever comes first. For patients who did not experience IAC-confirmed disease progression and death before the analysis cut-off date or the date of initiation of new anticancer treatment, PFS will be censored at the date of the last valid disease assessment not showing disease progression performed prior to initiation of a further anticancer treatment or the analysis cut-off date, whichever comes first.
- Overall survival (OS) (in months): defined as the time interval from the date of first isatuximab administration to death from any cause. In the absence of the confirmation of death before the cut-off date, OS will be censored at the cut-off date or at the last date the patient is known to be alive, whichever comes first.

- Time to response (TTR) (in weeks): TTR is defined as the time from first dose to first IAC response (PR or better) that is subsequently confirmed.
- Duration of follow-up (DFU) (in weeks): DFU is defined as the time from first dose to last response disease assessment before start of other therapy or cut-off date, whichever comes first.

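### The window for best overall response does not close at IAC-determined progression, so a confirmed response after progression would count in the primary ORR

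*SAP*

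**What the plan says.** **Response window.** Phase 2 SAP 2.1.3.1 defines ORR from BOR as assessed by the IAC. The BOR window opens when dosing begins and takes in assessments "through the entire study excluding any assessments performed after the cutoff date or following the start of further therapies for MM". These are the only two exclusions. The same section orders the categories from best to worst with sCR, CR, VGPR, PR, MR and SD all above PD. CBR in 2.1.3.2 uses the same BOR. Phase 1 SAP 2.1.3 has the same gap: its window runs "through the entire study excluding any time point following the start of other treatment for MM".

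**Progression in the time-to-event endpoints.** Under Phase 2 SAP 2.1.3.2, the first IAC-confirmed progression is a PFS event. DOR runs from the first confirmed response "to the date of first IAC determined PD or death, whichever happens earlier". Protocol 9.3.1 instead runs DOR "to the date of subsequent progressive disease (PD) or death, whichever happens earlier".

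**Stopping treatment.** Protocol 8.1.2 doses "until unacceptable toxicity, disease progression, withdrawal of consent and/or" the investigator's decision. The synopsis and sections 6.4 and 6.7.1 also let treatment run until progression. Section 11.1.1 lists progression as an example of the case where, in the investigator's "opinion, continuation of the study treatment would be detrimental to the" patient's wellbeing. No passage ties stopping to an IAC determination of PD.

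**The concern.** Once a patient has progressed, a response endpoint normally stops looking. Here the rule is stated positively, with two exclusions, and progression is not one of them. Because PR outranks PD, a confirmed PR after an IAC PD replaces that PD as the patient's BOR. The patient is then a responder in the primary analysis and a progression event in PFS, on the same committee's readings.

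The error can go only one way. Leaving the window open can add responders to ORR and CBR and can never remove one. The primary test turns on about eight responders, so a single such patient could matter. DOR for that patient also has no sensible value if the SAP wording is followed to the letter.

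**Working it through.** **1. Can an assessment after IAC PD exist?** Yes, while the patient is on drug.
- The endpoint uses IAC readings. Phase 1 SAP 2.1.3 says the site's own PD call is not used for efficacy, so the two determinations are separate.
- Myeloma laboratory tests are drawn before every cycle (flowchart footnote 21), so the IAC receives new data for as long as dosing continues.
- PD by imaging, marrow or hypercalcemia needs no confirmation (protocol 9.3.1), so one IAC reading can create a PD that the site does not share.
- Dosing can therefore continue after an IAC PD if the site did not call PD, or if the investigator continued under the wording of 11.1.1.

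**2. Do the response criteria block it?** Only in part. Appendix C lets the two consecutive assessments fall at any time before new therapy. Its one relevant bar on CR, PR and SD is progressive or new bone lesions. PD by paraprotein, soft-tissue plasmacytoma or hypercalcemia is not covered.

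**3. The plan's own threshold.** Inputs from protocol 13.1 and Phase 2 SAP 1.3: null ORR 10%, true ORR 28%, one-sided exact binomial test at 0.025, N = 33 to 36, rejection at 8 responders (8/33 = 24.2%). The formula is P(X ≥ k | N, p) = Σ from j = k to N of C(N, j) p^j (1 − p)^(N − j).

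With p = 0.10, P(X ≥ 8) is 0.0141, 0.0169, 0.0200 and 0.0235 for N = 33, 34, 35 and 36. Eight is the smallest count at or below 0.025 for every N in the range, so the threshold reproduces. The stated power of at least 80% reproduces only at N = 35 and 36 (80.5% and 83.0%, against 74.5% and 77.6% at N = 33 and 34). That is a separate matter and nothing here depends on it.

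**4. Effect of one reclassified patient.**

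| N | Responders | ORR | Exact p | 95% Clopper-Pearson | Null rejected |
|---|---|---|---|---|---|
| 33 | 7 | 21.2% | 0.0417 | 9.0 to 38.9% | no |
| 33 | 8 | 24.2% | 0.0141 | 11.1 to 42.3% | yes |
| 36 | 7 | 19.4% | 0.0628 | 8.2 to 36.0% | no |
| 36 | 8 | 22.2% | 0.0235 | 10.1 to 39.2% | yes |

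One patient moves ORR by 1/33 = 3.0 or 1/36 = 2.8 percentage points. Two patients move it by 6.1 or 5.6 points.

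**5. DOR for such a patient.** Assume the first IAC PD is on day 57 and a confirmed PR is first seen on day 85. Taken literally, the SAP gives (57 − 85)/7 = −4 weeks. Under the protocol's wording, only a PD after day 85 can end the response, so the value cannot be negative.

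**The case against.** The strongest reply is that patients should rarely get this far. Several passages say treatment runs until progression, and none provides for treatment beyond it. The clause in 11.1.1 on keeping patients on treatment concerns those who are clinically stable. After treatment ends, disease assessments are required only for patients with PR or better who stopped for a reason other than progression (flowchart footnote 23, sections 12.5 and 12.6). A patient stopped for PD has one end-of-treatment assessment, while a response needs two. Paraprotein PD is a numeric criterion, so lasting disagreement between site and IAC would have to be substantial, and the patient would then need a reduction of at least half. Protocol 9.3.1 gives BOR to the IAC, whose charter is not available and may stop adjudication at PD. All of this stands. It limits how often the problem can arise but does not close the window in the SAP.

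Three stronger readings are tempting and are not supported.
- *That the plan intends dosing after progression.* This is only an inference from the 11.1.1 wording and from the separation of site and IAC readings.
- *That the test exceeds its 0.025 level.* Suppose 1% or 2% of patients who did not respond before PD were later counted. With a pre-progression ORR of 10%, the counted rate is 0.10 + 0.90 × 0.01 = 0.109 or 0.10 + 0.90 × 0.02 = 0.118, and at N = 36 the chance of rejecting is 3.7% or 5.5% instead of 2.4%. But those rates are assumed, and the SAP's null concerns ORR as the SAP defines it. This is a difference between endpoint definitions, not type I error inflation for the stated endpoint.
- *That DOR will be negative.* The SAP says it is to be read with the protocol, which requires a subsequent PD. The negative value arises only on a literal reading of the SAP alone.

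**Conclusion.** The gap is real but conditional. As written, the Phase 2 SAP (and the Phase 1 SAP) would count a confirmed response after an IAC PD in BOR, and the Phase 2 SAP would carry it into the primary ORR and CBR while PFS already records an event. The direction is upward only.

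The frequency cannot be derived from the documents. It is probably low; 0 to 2 patients is an assumption, and zero is within it. The seven-versus-eight comparison shows that any one misclassified patient can decide the test at N = 33 to 36. It does not show that this rule will produce one. The conclusion rests on two conditions: that a patient stays on drug after an IAC PD, and that the IAC goes on adjudicating after its own PD call. The difference in DOR wording between SAP and protocol exists whatever the frequency.

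**What to change.** - In Phase 2 SAP 2.1.3.1 and Phase 1 SAP 2.1.3, end the BOR window (and so ORR and CBR) at the earliest of first IAC-determined PD, start of further myeloma therapy and cut-off.
- In Phase 2 SAP 2.1.3.2, end DOR at the first IAC PD after the response, or death, in line with protocol 9.3.1.
- List separately any response seen after an IAC PD.
- Reconcile protocol 8.1.2, the synopsis and 11.1.1 on whether progression by itself ends treatment. Which rule applies is for the sponsor and investigators to settle.

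The cost is two SAP definitions, one programming condition and one listing. The SAP needs revision anyway, since its section 4 puts the second cut-off at about 12 months and protocol 6.7.2 puts it at 20. The rationale for Amended Protocol 04 refers to results of the first analysis, so the change should be dated and ORR shown under both windows. The downside is that ORR may come out slightly less favourable.

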**Table 4 – List of variables for subgroup analyses**

Variable	Description
Age	<70 vs. $\geq$ 70
Number of previous lines of therapy	$\leq$ 6 vs. $>$ 6
Gender	Male vs. Female
ECOG PS	0-1 vs. 2
ISS staging at study entry	I vs. II vs. III
High risk cytogenetic	Yes vs. No
Baseline creatinine clearance	<60 ml/min/1.73m  vs. $\geq$ 60 ml/min/1.73m 
With plasmacytomas at screening	Yes vs. No

#### **2.1.3.2 Secondary efficacy endpoint(s)**

Secondary efficacy endpoints are defined below.

- Duration of Response (DOR) (in weeks): DOR is defined as the time from the date of the first IAC determined response ( $\geq$  PR) that is subsequently confirmed, to the date of first IAC determined PD or death, whichever happens earlier (if reported before the analysis cut-off date or the date of initiation of a new anticancer treatment). If progression and death are not observed before the analysis cut-off date or the date of initiation of new anticancer treatment, DOR will be censored at the earliest of the date of the last valid disease assessment not showing disease progression performed prior to initiation of a further anticancer treatment or the analysis cut-off date. DOR is determined only for patients who have achieved a confirmed response of  $\geq$ PR.
- Clinical benefit rate (CBR): defined as the proportion of patients with sCR, CR, VGPR, PR or MR as BOR according to IMWG criteria, as determined by the IAC.
- Progression free survival (PFS) (in months): defined as the time interval from the date of first isatuximab administration to the date of the first IAC-confirmed disease progression or the date of death due to any cause, whichever comes first. For patients who did not experience IAC-confirmed disease progression and death before the analysis cut-off date or the date of initiation of new anticancer treatment, PFS will be censored at the date of the last valid disease assessment not showing disease progression performed prior to initiation of a further anticancer treatment or the analysis cut-off date, whichever comes first.
- Overall survival (OS) (in months): defined as the time interval from the date of first isatuximab administration to death from any cause. In the absence of the confirmation of death before the cut-off date, OS will be censored at the cut-off date or at the last date the patient is known to be alive, whichever comes first.

- Time to response (TTR) (in weeks): TTR is defined as the time from first dose to first IAC response (PR or better) that is subsequently confirmed.
- Duration of follow-up (DFU) (in weeks): DFU is defined as the time from first dose to last response disease assessment before start of other therapy or cut-off date, whichever comes first.
- Best percent change in paraprotein: best percent change in paraprotein will be calculated for the measurable paraprotein parameter defined at baseline excluding anytime point following the start of other anticancer therapy.

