Bone marrow aspiration to be performed to confirm a CR and as clinically indicated. In case of dry-tap, bone marrow biopsy to be performed to confirm CR. Once CR is confirmed at a given time point, a consecutive assessment for immunofixation and free light chain is required.
22. Extramedullary Disease: Baseline to be performed within 21 days prior to study drug administration. If extramedullary disease present at baseline, to be performed approximately every 12 weeks (eg. at Cycle 4, 7, 10). To be performed upon clinical suspicion of progressive disease. This may include computerized tomography (CT) or magnetic resonance imaging (MRI) scan of the abdomen/pelvis, CT or x-ray of the chest, ultrasound of the liver/spleen or abdomen. May be omitted at End of Treatment if conducted within 12 weeks. All imaging will be sent to a central imaging lab.
23. Disease assessments during follow-up period are only required for patients with PR or better who have discontinued study treatment for reasons other than disease progression and have not yet started treatment with another anti-cancer therapy. Patients will be followed every 4 weeks for progression during this period. Disease assessments required every 4 weeks is myeloma-specific lab tests. Extramedullary disease assessment is required approximately every 12 weeks or upon clinical suspicion of progressive disease. All imaging will be sent to a central imaging lab. A bone marrow aspiration and/or biopsy, skeletal survey are only required if clinically indicated to confirm response or progression according to IMWG criteria.
Disease assessments not required once patient starts treatment with another anti-cancer therapy.
24. Skeletal survey and chest X-ray: X-ray to be performed at screening on all patients (the same methods must be used throughout the study). Repeat skeletal surveys are only required as clinically indicated. All imaging will be sent to a central imaging lab.
X-ray skeletal survey should include radiographs of the following: lateral skull; Postero-Anterior (PA) chest; Antero-Posterior(AP) and lateral cervical spine; AP and lateral thoracic spine; AP and lateral lumbar spine; AP pelvis; AP upper extremities, shoulder to elbow, bilateral; and AP lower extremities, hip to knee, bilateral.
Chest X ray: To be performed at screening for assessment of pulmonary disease condition and then as clinically indicated.

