Progression free survival (PFS): defined as the time interval from the date of first study treatment administration to the date of the first assessed disease progression or death due to any cause, whichever comes first. In the absence of disease progression or death before the analysis cutoff date, or the date of initiation of new anticancer treatment, PFS will be censored at the date of the last valid assessment performed before the cutoff date or the date of initiation of new anticancer treatment, whichever is earlier.

Time to progression (TTP): defined as the time interval from the date of first study treatment administration to the date of the first assessed disease progression. In the absence of disease progression before the analysis cutoff date, or the date of initiation of new anticancer treatment, TTP will be censored at the date of the last valid assessment performed before the cutoff date or the date of initiation of new anticancer treatment, whichever is earlier.

Response evaluation will include:

- M-protein quantification (serum and 24 hours urine)
- Serum free light chain (FLC) levels
- Bone marrow aspiration and/or biopsy
- CT/MRI scan of plasmacytoma (medullary and extramedullary)
- Bone skeletal survey
- Corrected serum calcium

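### Phase 2 PFS counts only IAC-confirmed progression, so a site progression that ends treatment but is not confirmed can be censored informatively, and no planned output shows the effect

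*SAP*

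**What the plan says.** **Event.** Protocol 9.3.1 measures PFS from first dose "to the date of the first assessed disease progression or death due to any cause, whichever comes first". That definition names no assessor. Phase 2 SAP 2.1.3.2 names one: PFS runs "to the date of the first IAC-confirmed disease progression or the date of death due to any cause".

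**Censoring.** Under the same SAP section, a patient with neither event before cut-off or new anticancer treatment is handled as follows: "PFS will be censored at the date of the last valid disease assessment not showing disease progression", counting only assessments made before new therapy or cut-off.

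**Stopping treatment.** Protocol 11.1.1 lists the grounds for permanent discontinuation. One begins "If, in the Investigator's opinion, continuation of the study treatment would be detrimental to the patient's wellbeing, such as", and disease progression is the first example under it. IAC agreement is not mentioned.

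**Assessment after stopping.** Protocol 1.6, footnote 23, makes disease assessment in follow-up "only required for patients with PR or better who have discontinued study treatment for reasons other than disease progression". Sections 12.5 and 12.6 repeat this. An end-of-treatment visit 30 ± 7 days after the last dose includes myeloma laboratory tests (12.4).

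**Confirmation.** Paraprotein progression needs two consecutive assessments (Phase 2 SAP 2.1.3; Protocol 9.3.1). Progression on imaging, marrow or calcium does not need confirming (Protocol 9.3.1).

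**Analysis.** PFS is estimated by Kaplan-Meier (Phase 2 SAP 2.4.4.2). Section 2.4.4.4, for additional efficacy analyses, is marked not applicable. No output uses or counts site-assessed progressions.

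**The concern.** The endpoint and the conduct rules rest on different assessors. The IAC decides whether a PFS event has occurred, while the investigator decides whether the patient stops treatment for progression, and with it whether later assessments are scheduled. When the two disagree, the patient is censored because the treating physician thought the disease was progressing. Kaplan-Meier assumes that a censored patient has the same future risk as those still under observation. That assumption is doubtful here.

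PFS is a secondary endpoint without a hypothesis test, but it is a main product of the second cut-off. Protocol 6.7.2 sets that cut-off at 20 months after the last patient's first dose for the final time-to-event analysis, and the amendment 04 rationale (Appendix J) says its purpose is mature PFS and OS. The confidence interval around the median reflects sampling error only and would not show this bias.

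**Working it through.** The documents give no PFS median, event count or IAC/site discordance rate, so there is no planned figure to reproduce. The check has three parts.

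**1. Path of one patient.** The site calls progression and stops treatment (11.1.1). The end-of-treatment visit follows (12.4). Footnote 23 then requires nothing further, because the reason for stopping was progression. There are three outcomes:

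- The IAC confirms progression, possibly using the end-of-treatment value: PFS event.
- The IAC does not confirm, and the patient dies before new therapy and cut-off: PFS event, but late.
- The IAC does not confirm, and no such death occurs: censored at the last assessment not showing progression.

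The third outcome is the problem.

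**2. Is the confirming laboratory value always drawn?** Section 12.4 lists M-protein quantification at the end-of-treatment visit without condition. Footnote 21 asks for electrophoresis and the 24-hour urine at discontinuation only if the last tests were more than 4 weeks (28 days) earlier. Timing, ignoring the visit windows on dosing days:

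- Site stops on pre-dose Day 1 labs, Cycle 3 or later. The last dose was Day 15 of the previous cycle, 14 days before. The visit falls 30 - 7 - 14 = 9 to 30 + 7 - 14 = 23 days after those labs.
- Same at Cycle 2 Day 1. The last dose was Day 22, 7 days before. The visit falls 16 to 30 days after the labs.
- That day's dose is given before the result is known. The visit falls 23 to 37 days after the labs.

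In the first case footnote 21 never calls for a repeat, while 12.4 does. In the other two it depends on the date. The two texts disagree on whether the second value is required.

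**3. Size.** Assumptions: exponential time to first event with true median m, and a constant share d of true first events that are site-called progressions, not confirmed by the IAC, and censored. With hazard λ = ln 2 / m, the observed event hazard is (1 - d)λ. Kaplan-Meier then estimates exp(-(1 - d)λt), whose median is m/(1 - d). The table gives the formula and, after the slash, a simulated Kaplan-Meier median (400,000 patients, near-continuous assessment, cut-off 20 to 32 months after first dose, new therapy at once), in months.

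| d | 1/(1-d) | m = 3 | m = 5 | m = 8 |
|---|---|---|---|---|
| 5% | 1.05 | 3.16 / 3.16 | 5.26 / 5.28 | 8.42 / 8.42 |
| 10% | 1.11 | 3.33 / 3.36 | 5.56 / 5.56 | 8.89 / 8.86 |
| 20% | 1.25 | 3.75 / 3.74 | 6.25 / 6.28 | 10.00 / 10.00 |
| 30% | 1.43 | 4.29 / 4.30 | 7.14 / 7.18 | 11.43 / 11.44 |

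Two variations at m = 5:

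- *Later deaths count.* If 30% of unconfirmed patients take no new therapy and their deaths count (assumed median 12 months to death), the medians are 5.60, 6.32 and 7.24 at d = 10%, 20% and 30%. The late events do not repair the estimate.
- *Assessments every 28 days (0.92 months).* The median falls on a visit: 5.52 at both d = 0 and 10%, 6.44 at 20%, 7.36 at 30%. A 10% discordance may then leave the reported median unmoved.

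If all 33 patients had an event, d = 10%, 20% and 30% would mean 3.3, 6.6 and 9.9 patients.

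**The case against.** PFS by independent review is a legitimate prespecified choice, and Protocol 6.9.2 gives the IAC ongoing responsibility for assessing response by IMWG criteria. The IAC charter is not among the documents and may say how disagreement with sites is handled. The end-of-treatment tests can supply the second paraprotein value, imaging goes to a central laboratory, and some progressions need no confirmation, so true discordance may be small. If the IAC is right and the open-label site wrong, the upward bias shrinks and counting site calls would bias PFS downward. All of this stands. It limits the size of the problem and supports keeping IAC-based PFS as the main analysis. It does not give the reader a count of discordant patients or any bound on their effect.

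Four stronger readings are tempting but are not supported:

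- *The plan says that the site call is unused in Phase 2.* The explicit sentence, that progression assessed "by the site doctor (collected in e-CRF) will not be used for phase 1 in efficacy analysis", is in the Phase 1 SAP (2.1.3) and covers phase 1 only. For Phase 2, non-use is an inference from the event definition and the absence of any other analysis.
- *Assessment ends at the site's call, and every unconfirmed call is censored.* The end-of-treatment tests come later, and death before new therapy and cut-off is an event.
- *DOR is biased upward too.* Protocol 13.4.8.3 plans Kaplan-Meier for DOR, but Phase 2 SAP 2.4.4.2 summarises it with descriptive statistics. There, censoring at the last assessment without progression records the same or a shorter duration.
- *The follow-up stop condition should be rewritten around IAC progression.* That wording reaches only patients with PR or better. At the design ORR of 28%, about 0.28 × 33 = 9 patients would qualify and about 24 would not. It would also need IAC feedback to sites, which the documents do not describe.

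**Conclusion.** The point holds for Kaplan-Meier PFS in Phase 2. A site-assessed progression that ends treatment and is not confirmed by the IAC can become a censored time, the censoring is informative if the call is a true progression, and nothing planned reveals how often this happens. The inflation of 11%, 25% and 43% at d = 10%, 20% and 30% is an illustration. It rests on an assumed discordance, exponential times, and every unconfirmed call being a true progression, so it should not be read as an estimate for this trial. False-alarm calls would make the bias smaller. The primary ORR analysis is untouched, and the point does not extend to DOR as the Phase 2 SAP analyses it. This is a worthwhile, inexpensive addition for a secondary descriptive endpoint; it does not invalidate the plan.

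**What to change.** Keep IAC-based PFS as the main analysis. In Phase 2 SAP 2.4.4.2, add:

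- one sensitivity Kaplan-Meier PFS analysis whose event is the earliest of IAC progression, site-assessed progression that ended treatment, or death;
- the number of patients censored in the IAC analysis after a site-assessed progression.

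The cost is one extra table. Reasons for treatment discontinuation are already to be summarised (Phase 2 SAP 2.2), and the Phase 1 SAP describes the site progression call as collected in the e-CRF; check that the Phase 2 e-CRF also holds it with a date. The sensitivity estimate may be biased downward if site calls are false alarms, so the two estimates should be read as a range.

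Separately, reconcile footnote 21 of Protocol 1.6 with section 12.4 on whether the myeloma laboratory tests at the end-of-treatment visit depend on the age of the last tests. No change to the post-treatment follow-up rule is proposed.
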